procedure with will equate study conditions based upon 1) age discrepancy between partners, 2) relationship length, and 3)

race and ethnicity using Qualtrics.

DATA COLLECTION: Participants have the options to first complete a CASI at home

before their BL appointment (or during BL if they have not done so beforehand). All other aspects of data collection occur at Hunter College. A second CASI survey will also be administered at the BL appointment. Time line follow back interviews to assess drug use, sexual behavior and PrEP adherence (where applicable) will at all assessments. Drug screening and PrEP adherence will be accomplished by obtaining fingernail samples from participants at all assessments. Blood will be collected for

testing PrEP medication adherence. STI testing will be

accomplished by collecting urine and rectal samples at BL, 6m, and 12m. HIV testing will be conducted at BL, 6m, and 12m.

Post-COVID: Participants receive a CASI link via email and an athome STI and HIV testing kit, a dried blood spot (DBS) collection kit for PrEP adherence, and a fingernail collection kit for drug screening (via regular mail) prior to assessment appointments.

All other aspects of data collection occur remotely via HIPAA-compliant Zoom.

OBJECTIVES:

- 1) Evaluate the efficacy of PARTNER in regards to three primary outcomes: 1) PrEP uptake and adherence 2) sexual transmission risk behavior and 3) drug use.
- 2) Identify individual and relationship factors which moderate/mediate intervention efforts.
- 3) Gather ideographic data to inform a future effectivenessimplementation study.
- 4) Validate the use of fingernail assays as a biological marker for PrEP adherence.

STUDY DESIGN

[figure not shown]
[figure not shown]

Figure 3. Participation timeline

- ^a To detect drug use for all participants and PrEP adherence for those on PrEP.
- ^b Gathered only for those on PrEP

STUDY TIMELINE

STUDY POPLUATION

Inclusion and Exclusion Criteria:

Participants who express interest in PARTNER must demonstrate the following inclusion criteria to be enrolled in the study:

- 18 29 years old; or 30-34 with a partner who is 18-29 (inclusive)
- Have a main partner who is another male for 1 month or longer
 - Main partner must be 18 years old or older
- Be HIV negative (as confirmed by rapid test)
- Have used drugs in the past 30 days
- Have engaged in TRB in the past 30 days

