Participants are considered enrolled in the study when they have completed informed consent. Randomization occurs immediately after the baseline appointment.

Informed Consent Process

Details of the study are reviewed with the prospective study participant by a research assistant who is trained and cleared to conduct assessments and is knowledgeable about the research study. This discussion is a critical component of the consent process and the prospective study participant will be given adequate time for this discussion and to read the written consent form. The research assistant is available to answer questions about the study including participant responsibilities, benefits, risks, and alternatives. The participant reviews the consent form and it is signed and dated by both the participant and study staff member conducting the assessment. A copy of the signed consent form will be given to the participant and the original will be kept securely by the project coordinator separate from other assessment materials.

Post-COVID: Participants review written consent information prior to their baseline appointment. The baseline survey link directs participants to a landing page containing detailed consent information. At the beginning of the baseline assessment, study staff provides an oral review of consent information and confirms age eligibility via Zoom. After reviewing this information, participants are asked to affirm their consent/assent to participate. A copy of the electronic consent form is emailed to the participant upon request.

Randomization Process/Systems

Participants are randomized at the end of their baseline assessment into one of two intervention conditions: 1) delivery of the 4 session PARTNER intervention or 2)

delivery of 4 education sessions. Each participant's condition is tracked in the access tracking database maintained by the project manager.

The study employs a stratified block randomization procedure with equate study conditions based upon 1) age discrepancy between partners, 2) relationship length, and 3) race and ethnicity using Qualtrics.

Schedule of Assessments

Sessions occurs approximately once per week for three weeks beginning one week after completion of the baseline assessment and session 1. There is a 12 week window for intervention completion, i.e. all four sessions must be completed within 12 weeks of the baseline assessment.

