Self-reported CAS with casual partners was corroborated by bacterial STI diagnosis. Participants were indicated as having a bacterial STI if they received a positive result for rectal or urethral gonorrhea or chlamydia at baseline, 6, or 12-month follow-up or if they self-reported receiving a diagnosis in the past 3 months at any assessment point. At baseline, 30.5% of those who

reported CAS with a casual partner had a bacterial STI compared to 7.7% of those who did not. Similarly, 44.2% of participants who reported having CAS with a casual partner at either the 3 or 6-month follow-up had a bacterial STI, compared to 23.9% of those who did not. Finally, 39% of those who reported having CAS with a casual partner at the 9 or 12-month follow-up had a bacterial STI compared to 9.5% of those who did not.

Detailed analytic plan

A series of bivariate analyses ($\chi 2$ tests of independence and independent samples t-tests) conducted in SPSS (version 29) evaluated the success of randomization and the presence of differential attrition. The generalized linear model function in SPSS was used to evaluate between-condition differences in baseline frequency of primary outcomes with count distributions (cannabis use days, other illicit drug use days, sexual HIV TRB) and baseline odds of PrEP uptake (a dichotomous variable).

Outcome analyses were conducted using piece-wise latent growth curve (LGC) models following procedures outlined by Chou et al. Growth trajectories over time following the delivery of an intervention may be characterized by a large initial response followed by a more sustained trajectory with a less dramatic slope. Piece-wise LGC models quantify this kind of trajectory using two slopes. Slope 1 quantifies the change from baseline to the immediate post-test (3-month follow-up). Meanwhile, Slope 2 quantifies the trajectory over the post-intervention follow-up period.

Two models were calculated for each outcome. Model 1 included the main effect of treatment on growth factors. Model 2 added the main effects of moderators (communication skills and relationship quality) as well as the interaction terms between these moderators and the main effect of treatment.

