Several considerations led to the inclusion of model covariates. Consistent with guidance for the analysis of data from randomized controlled trials that utilize stratified randomization (16), stratification variables were included as covariates in regressions predicting latent growth factors. The COVID-19 pandemic and recovery corresponded with changes in substance use and sexual behavior among SMM. To account for this, models incorporated a dichotomous, timevarying predictor indicating whether an assessment occurred before or after March 2020. All models were calculated using full-information maximum likelihood estimation in Mplus Version 8.0. This permitted the retention of all randomized cases consistent with the intent-to-treat paradigm. Model significance was evaluated using a robust log-likelihood $\chi 2$ test comparing the log-likelihood of the specified model to a null-model – in which all structural coefficients associated with the regression of latent growth factors on condition and site were constrained to be zero. Where model results were significant, the effect of the PARTNER intervention was evaluated by examination of regression parameters for Slopes 1 and 2. Given the directional nature of hypotheses, single-sided p-values were used to determine the

significance of the intervention effect. When evaluating the significance of putative moderators and associated interaction terms, two-sided p-values were used.

Power analyses

We utilized the *Test for the Ratio of Two Negative Binomial Rates* module in PASS 19 to evaluate power to detect between-condition differences in drug use frequency at any one follow-up time point. Power (1-beta) was set to .80 and the probability of type II error (alpha) was set to .05. The number of exposures was set to 30 (the number of days of use assessed in the TLFB). The rate of use in the education condition was set to 3, 6, and 9. Meanwhile dispersion values of 1, 2, and 4 were tested. Power was highest at low levels of dispersion and high based rates of use in the education condition. Under these circumstances, the study has power=.80 to detect a rate ratio of 0.70 or a 30% reduction in drug use instances. At high levels of dispersion and low base rates, the study would be expected to detect a rate ratio of 0.48.

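### The test that opens each efficacy evaluation constrains an undefined site term together with condition, and no arm difference at 12 months is specified

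*Combined protocol and SAP*

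**What the plan says.** The Detailed analytic plan fits a piece-wise latent growth curve to each outcome. Slope 1 runs from baseline to 3 months and Slope 2 covers the later follow-up.

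- **Model terms.** "Model 1 included the main effect of treatment on growth factors". Model 2 adds the moderators and their interactions with treatment. In addition, "stratification variables were included as covariates in regressions predicting latent growth factors", and a time-varying indicator marks assessments before or after March 2020.
- **The gate.** Each model is compared with a null in which "all structural coefficients associated with the regression of latent growth factors on condition and site were constrained to be zero". Only where that comparison is significant is it the case that "the effect of the PARTNER intervention was evaluated by examination of regression parameters for Slopes 1 and 2". The slope p-values for the intervention are one-sided.
- **Stratification.** Randomization Process/Systems describes a "stratified block randomization procedure with equate study conditions based upon 1) age discrepancy between partners", relationship length, and race and ethnicity.
- **Location.** The Study Abstract says of the in-person period that, apart from an optional at-home survey, "All other aspects of data collection occur at Hunter College". Conduct later moved to Zoom.
- **Timing.** "Randomization occurs immediately after the baseline appointment".
- **Alpha.** Power analyses says "the probability of type II error (alpha) was set to .05". No level is given for the gate or the slope tests.
- **Hypothesis.** The Quantitative Analysis Plan expects more PrEP initiation or adherence over the whole of follow-up.

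**The concern.** The gate decides which outcomes receive an efficacy evaluation at all, so a reader must be able to tell what it tests. A nuisance factor constrained to zero alongside treatment makes the gate answer a mixed question. A prognostic site could open it with no treatment effect, and an irrelevant site adds degrees of freedom and costs power. Even with site removed, a test on all three growth factors includes the arm difference at baseline, which precedes randomization.

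The second issue is what is reported once the gate is open. Slope 1 describes the early change. Slope 2, tested one-sided, cannot declare a loss of benefit. Nothing combines the two into an arm difference at the last visit, so a published early gain could stand without an interval for what is left at 12 months.

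**Working it through.** **1. Where site appears.** It is absent from Model 1, the stratification factors and the covariates listed in the Detailed analytic plan. Schedule of Assessments and Managing and Tracking Study Visits mention site staff. The safety and consent sections mention site investigators. Equivalency Checks plans a cross-site baseline comparison and says that differences found will be controlled for later. No section defines or counts sites.

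**2. Degrees of freedom.** There are three growth factors (intercept, Slope 1, Slope 2). Condition only: 3 × 1 = 3 df. Condition plus a two-level site: 3 × 2 = 6 df. More sites give more.

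**3. The plan's nearest figure.** Power analyses gives detectable drug-use rate ratios of 0.70 and 0.48 at one follow-up time point. With |ln RR| = (1.960 + 0.842) × √[(1/μ + 1/(μ·RR) + 2k)/120] and μ = rate × 30, I get 0.696 (rate 9, dispersion k = 1) and 0.484 (rate 3, k = 4). These agree and are not disputed. They power a difference at one visit, which the analysis section does not specify.

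**4. Gate power (illustration).** Assumptions:
- 120 per arm, five waves, Gaussian data with known covariance.
- Compound symmetry or AR(1), correlation .25, .50 or .75.
- Retention full, or falling to 80% (1, .95, .90, .85, .80): 12 scenarios in all.
- Loadings: intercept 1; Slope 1 (0,1,1,1,1); Slope 2 (0,0,1,2,3).
- Slope 1 effect δ set to 80% power on 1 df (noncentrality 7.849), Slope 2 effect zero, gate alpha .05.

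With I the information matrix for the three condition effects, the gate's noncentrality is λ = (0, δ, 0) I (0, δ, 0)ᵀ. Power is the upper tail of a noncentral χ² beyond 7.815 (3 df), 12.592 (6 df) or 5.991 (2 df). In the least favourable scenario (AR(1), .75, 80% retention) λ = 10.40, which gives .779, .664 and .831. In the most favourable (AR(1), .25, full retention) λ = 31.67, which gives .999, .996 and .9995.

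| Gate | Power, 12 scenarios |
|---|---|
| Condition only, 3 df | .779-.999 |
| Condition plus null two-level site, 6 df | .664-.996 |
| Two slopes, intercept path free, 2 df | .726-.841 |
| Two slopes, intercept path fixed at zero, 2 df | .831-.9995 |

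The third row is the weak one because the intercept and Slope 1 effect estimates correlate at −.35 to −.66. Freeing the intercept path discards that information.

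**5. Gate plus Slope 1 test.** 3 df, one-sided: 75-88%. 2 df with fixed path, two-sided: 79-96%. A check with overdispersed counts (base rates 3, 6, 9; rate ratio .70, or .75 at rate 9; 80% retention) is lower: 46-62% and 54-72%.

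**6. Error across outcomes under the null**, as 1 − (1 − p)⁴ for four outcomes taken as independent:

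| Rule | Any false result |
|---|---|
| 3 df, one-sided slopes, favourable | 8.8-9.2% |
| 2 df fixed, one-sided slopes, favourable | about 11-12% |
| 2 df fixed, two-sided slopes, favourable | 9.5-9.7% |
| 2 df fixed, two-sided slopes, either direction | 13.7-16.5% |
| As row 3, plus an ungated 12-month test, favourable | 15-16% |

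**7. Fading.** The 12-month log effect is the Slope 1 effect plus 3 × the Slope 2 effect, with no intercept difference. With RR 0.70 at 3 months, ln 0.70 = −0.357. A Slope 2 effect of +0.357/3 = +0.119 per quarter gives 0.70, 0.79, 0.89 and 1.00 at 3, 6, 9 and 12 months. Under step 4's assumptions and the 3-df rule, Slope 1 is still declared in 69-87% (half the benefit lost) or 72-83% (all lost). With the intercept path fixed, a two-sided 95% interval at 12 months lies wholly on the favourable side in 50-96% if benefit is maintained, 16.5-46.6% if half is lost and 2.5% if all is lost.

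**The case against.** Site may simply be stray wording, in which case part of the remedy is to delete a word. That is fair, but the deletion is still needed, and the intercept would remain in the gate. The control rule in Equivalency Checks offers a route by which site could enter. That route is conditional, leaves site undefined and does not explain constraining a nuisance term in an efficacy test.

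A reader might infer that the gate inflates false positives. If a true site effect sat in all four models, error across outcomes could reach 15-34%. The documents do not support this: no passage shows a site effect or a fitted site term, and the slope tests behind the gate are specific to treatment.

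A reader might also infer that the plan hides fading or ignores a 12-month primary endpoint. Neither follows. The Slope 2 estimate remains visible, and a Slope 1 finding is correct if the 3-month benefit is real. No section makes 12 months the primary time point. The whole-of-follow-up wording concerns PrEP and could mean an average, and the plan expects a flatter later course. The plan also gives a reason for one-sided tests. What stands is narrower: no interval for the final visit is specified.

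**Conclusion.** The point holds and should be fixed. The gate as worded is neither specific to treatment nor reproducible. If a null two-level site is in the model, the cost is up to about 11 points of gate power (77.9% to 66.4% in the least favourable scenario) and very little in the most favourable. If site is stray wording, the remaining defect is that a baseline difference is tested as though it were efficacy. The missing 12-month estimate is a reporting gap, not an error in the slope tests.

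The power figures are Gaussian illustrations with assumed covariances and time scores. The count check is lower throughout, and no check was made for the binary PrEP outcome. The error figures assume four independent outcomes, although the Primary outcomes section sets transmission risk to zero for men prescribed PrEP who missed 13 doses or fewer, which links two of them. The gain is a clear gate, some power and a visible 12-month estimate. It is not lower error across outcomes. Nor would a 12-month interval that includes no difference prove lost benefit, since a maintained effect can be missed half the time.

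**What to change.** 1. Delete site from the null model. If sites exist, define site and leave it free in both the null and the fitted model, and reconcile this with Equivalency Checks.
2. For Model 1, define the gate as condition-to-Slope 1 = condition-to-Slope 2 = 0 (2 df), with covariates free and the condition-to-intercept path fixed at zero in both models, since randomization follows baseline. If that path is to stay free, keep a condition-only 3-df gate, because a 2-df gate would then lose power. For Model 2, state which coefficients the null constrains.
3. State alpha (.05) for the gate and the slope tests, and correct its label in Power analyses.
4. Report the model-implied arm difference at 12 months with a two-sided 95% CI for each outcome, as an estimate beside the slopes and not as a further ungated test.
5. Because the document already reports data, date the change and show results under the present rule alongside.

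Two-sided slope p-values are optional. Whichever choice is made, state the matching error from step 6 of the working, including the rise to about 11-12% if one-sided slopes are kept behind the 2-df gate.

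Cost: SAP wording, one re-specified likelihood-ratio test and one contrast per outcome, with no new data. The fixed intercept path relies on sound randomization; the planned baseline comparison can stay as a description, with its role under Equivalency Checks made clear.

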Power to detect differences in HIV transmission risk behavior was calculated in 2 ways. First, using procedures similar to those described for drug use, the study has power to detect a rate ratio between 0.48 and 0.69 in the number of CAS events in the absence of PrEP. This calculation tested average rates of CAS in the absence of PrEP in the education condition of 1, 3, and 5 instances and dispersion was tested at values of 1, 2, and 4. Power to detect significant differences in the odds of a positive STI test was calculated using the *inequality tests for 2 proportions in a repeated measures design* module [60]. Analyses specified 4 waves of data, power (1-beta) was set to .80, and the probability of type II error (alpha) was set to .05. Autocorrelation (rho) was permitted to vary between .25 and .75. The proportion of positive STI diagnosis in the education condition was tested at values of .13, .10, and .07. Power declined as rho increased. Power increased with the proportion of positive diagnoses in the education condition. Analyses suggested that the study is adequately powered to detect large effects, associated with an odds ratio between 0.20 (under the least favorable conditions) and 0.32 (under the most favorable).

Power to detect differences in PrEP uptake was similarly calculated using the *inequality tests for 2* proportions in a repeated measures design module [60]. Analyses specified 4 waves of data, power (1-beta) was set to .80, and the probability of type II error (alpha) was set to .05. Autocorrelation (rho) was permitted to vary between .25 and .75. We estimated that on average 35% of the education condition would be on PrEP during the follow-up period. The proposed sample is sufficient to detect an odds ratio

of 1.90 even at the highest values of rho, which corresponds to approximately 51% of the PARTNER condition initiating PrEP. With regard to adherence, assuming approximately 100 participants (45% of the sample assuming 80% retention) are on PrEP at any follow-up point and 75% of the control condition is adherent to their PrEP medication (Cronbach alpha=.05; and ρ =.25 to .50), results suggested that the study has power=.80 to detect an odds ratio of approximately 3.0.

Equivalency Checks

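### PARTNER is judged by one-sided p-values on two slopes with no comparison of levels, so the slope tests cannot declare harm and recovery from early harm can test as benefit

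*Combined protocol and SAP*

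**What the plan says.** The rule is in the Quantitative Analysis Plan, under Detailed analytic plan. Each outcome gets a piecewise latent growth model. Slope 1 runs from baseline to the 3-month post-test, and "Slope 2 quantifies the trajectory over the post-intervention follow-up period". The expected shape is a "large initial response followed by a more sustained trajectory with a less dramatic slope".

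The first step is a log-likelihood chi-square test against a null model "in which all structural coefficients associated with the regression of latent growth factors on condition and site were constrained to be zero". Then: "Where model results were significant, the effect of the PARTNER intervention was evaluated by examination of regression parameters for Slopes 1 and 2". On sidedness the text reads "Given the directional nature of hypotheses, single-sided p-values were used to determine the" and continues, over a page break, "significance of the intervention effect. When evaluating the significance of putative moderators and associated interaction terms, two-sided p-values were used".

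The hypotheses at the start of the same section all point towards benefit. They concern levels or probabilities: PrEP initiation or adherence across follow-up, lower probability of transmission risk behaviour, and less drug use than Education. None concerns the rate of change after 3 months.

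The plan does not state a significance level for the slope tests, a rule for a wrong-direction effect, a rule for combining the slopes, or a between-arm contrast at 12 months or averaged over follow-up.

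**The concern.** A one-sided test towards benefit has no rejection region for harm. Harm cannot be ruled out in advance here. The comparator is four active education sessions on HIV risk and drug use, and the Primary limitations section itself lists limited efficacy data for PARTNER. More drug use, more condomless sex or poorer PrEP adherence than under Education are all possible. The chi-square test that opens the way to the slopes has no direction, so harm can help to open it.

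The second issue is what Slope 2 means. An early benefit that is held gives no Slope 2 effect, and one that partly fades gives an adverse Slope 2 effect. Early harm that wears off gives a favourable one. The stated hypotheses therefore do not fix the sign of Slope 2, and directional hypotheses do not justify a one-sided test of it. At stake is a positive finding on a primary outcome in a trial where PARTNER was never better than Education at any assessment.

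**Working it through.** **The plan's own power figure.** It does not settle the intended sidedness. For drug use the Power analyses section gives power .80, alpha .05 and exposure 30, with detectable rate ratios of 0.70 (best case: rate 9, dispersion 1) and 0.48 (worst case: rate 3, dispersion 4). The check uses a Wald test on the log rate ratio, with variance [(1/μ1 + 1/μ2)/30 + 2k]/n.
- Two-sided .05, n = 120 per arm: ratio 0.70 gives SE .1294, and Φ(.3567/.1294 − 1.960) = .787. Ratio 0.48 gives SE .2588, and Φ(.7340/.2588 − 1.960) = .810.
- One-sided .05, n = 96 per arm (80% retention): Φ(.3567/.1447 − 1.645) = .794 and Φ(.7340/.2893 − 1.645) = .814.

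Both readings fit. For the binary outcomes the plan names a module for "inequality tests for 2 proportions in a repeated measures design" without stating sidedness.

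**Set-up for the slope rule.** From the documents: 240 participants, equal allocation, five waves, slopes meeting at 3 months. Assumed: normal outcome with SD 1, known correlation, model test on 3 df (condition on intercept, Slope 1 and Slope 2) at .05, and slope tests at .05. The five between-arm differences have covariance (2/120) × R. Generalised least squares gives the intercept, Slope 1 and Slope 2 contrasts, with Slope 2 scaled as total change from 3 to 12 months. The scenario has no baseline difference, PARTNER 0.3 SD worse at 3 months, and a linear return to no difference at 12 months. The true contrasts are (0, 0.3, −0.3). There were 400,000 draws per row.

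**Hand check** (compound symmetry, .5, ignoring the model test). Two-sided harm test on Slope 1: Φ(0.3/.1190 − 1.960) = .71. One-sided benefit test on Slope 2: Φ(0.3/.1225 − 1.645) = .79.

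**Results with the model test kept:**

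| Correlation | Model test significant | Slope 1 harm, two-sided .05 | Slope 2 favours PARTNER, one-sided .05 | Slope 2 favours PARTNER, two-sided .05 |
|---|---|---|---|---|
| Compound symmetry .25 | 62.7% | 46.1% | 50.7% | 44.5% |
| Compound symmetry .5 | 74.3% | 63.6% | 66.9% | 61.7% |
| Compound symmetry .7 | 91.2% | 86.5% | 88.1% | 85.0% |
| AR(1) .5 | 62.9% | 54.0% | 44.4% | 37.0% |
| AR(1) .7 | 81.8% | 77.4% | 59.8% | 50.3% |

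Under the plan's tests the Slope 1 harm is declared in 0% throughout.

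**Three further checks.**
- Level contrast: the true baseline-to-12-month difference is 0.3 − 0.3 = 0, so a two-sided .05 test favours PARTNER in 2.5%. Averaged over the four follow-ups, PARTNER is truly worse by (.3 + .2 + .1 + 0)/4 = .15 SD.
- Cause: the slope estimates correlate at −.51 (compound symmetry) or about −.2 to −.3 (AR(1)). If the 0.3 SD harm persists, so that the true Slope 2 effect is zero, Slope 2 favours PARTNER in only the nominal 5%. The sampling correlation is therefore not the driver. The test correctly detects a real Slope 2 difference that is not a benefit in level.
- Full null: any efficacy call on either slope occurs in about 2.4% per outcome with the model test, and about 10% without it.

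**The case against.** A declared one-sided test of stated directional hypotheses is a known, if debatable, choice, and a reader can double the p-value. The plan examines both slopes. A reader might infer that it treats a favourable Slope 2 alone as efficacy, or that an adverse Slope 1 would go unreported, but no text says either. What is missing is a decision rule, and harm could still be seen in the estimates. This part of the objection stands and limits the point to the formal tests.

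A reader might also infer that the rule amounts to two-sided .10 testing and inflates false positives. The documents do not support that. No alpha is given for the slope tests, and the preceding model test holds null efficacy calls to about 2.4% per outcome under the assumptions above.

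Nor is sidedness, or the 3-month wave shared by the slopes, the cause of the recovery problem. Two-sided testing removes only about 3–5 points under compound symmetry at .5–.7 (7–9 under AR(1)), and persistent harm leaves Slope 2 at its nominal rate.

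The magnitudes are also conditional. The outcomes are counts and a dichotomy, no passage supports a 0.3 SD reversal, and the model-test null covers site as well as condition, so it may have more degrees of freedom and reject less often. The objection does not remove either consequence. The model test is no safeguard against them, because early harm itself helps to make it significant.

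**Conclusion.** The point holds as two separate defects. First, the one-sided slope tests cannot declare an adverse PARTNER effect. In the scenario above, a two-sided .05 test on Slope 1 would declare it in about 64–87% (compound symmetry, .5–.7) or 54–77% (AR(1)) of trials. Second, Slope 2 is tested without reference to level, so recovery from early harm can be significant in PARTNER's favour: 67–88% or 44–60%, and 51% at compound-symmetric .25. Changing sidedness cures the first defect but not the second.

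The effect size, normal outcome, correlation structure, degrees of freedom of the model test and .05 level for the slopes are assumptions. They set the percentages, not the direction of the problem. The plan should be changed here, but this is neither a general type I error failure nor evidence that harm would be concealed.

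**What to change.** In the Detailed analytic plan:

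1. Report two-sided p-values at a stated .05, with 95% confidence intervals, for condition on Slope 1 and Slope 2. State that an adverse effect will be reported as such.
2. Base the efficacy conclusion on the model-implied between-arm difference in change from baseline to 12 months, or averaged over follow-up, and name one of the two. It comes from the same model. With Slope 2 scored per three-month interval, it is the Slope 1 effect plus 3 times the Slope 2 effect (12 months), or plus (0 + 1 + 2 + 3)/4 = 1.5 times (average).
3. State that when the Slope 1 point estimate is adverse, a favourable Slope 2 does not count as efficacy unless that contrast also favours PARTNER.

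The section is written in the past tense. If the models have already been run, label the contrast as added afterwards.

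The cost is analysis wording and one extra contrast, with no new data. A benefit with power .80 at one-sided .05 has Φ(1.645 + 0.842 − 1.960) = .70 at two-sided .05. The 12-month contrast has the same standard error as Slope 1 under compound symmetry (.119 at .5) but a larger one under AR(1) (.176 against .128 at .5).
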